
10. DATA COLLECTION AND QUALITY ASSURANCE

10.1 Data Collection Forms

Information is provided by participants through written responses to questionnaires, and through physiological measures of cortisol (saliva) and heart rate variability. The self-report measures will be assessed at baseline, week 6, and week 12, with the exception of the Hot Flash Daily Diary which will be completed daily from baseline through week 6, and for one week at week 12. The Self-Hypnosis Practice Log will be completed daily during weeks 1 through 6 of the intervention and again during week 12. Physiologic measures will be collected at baseline and week 6.

Baseline questionnaires will be completed in the lab during the baseline interaction. During the COVID-19 restrictions, the questionnaires will be mailed to the participant with postage-paid envelope for return or sent electronically. The baseline Hot Flash Daily Diary, cortisol collection, and HRV data will be collected at home during the 7 days following the baseline interaction. The baseline hot flash diary, saliva kits and HRV monitor will be given to the participant at the baseline interaction (or mailed to the participant during the COVID-19 restrictions) with comprehensive education about the data collection. The HRV monitor will be worn for the designated time during the two days of cortisol collection. A second interaction within 30 days of the baseline data collection will be scheduled and serve as the

randomization/education interaction. At this visit, participants will be given a Toolkit which will include:

- Intervention materials
 - o weekly education/instruction booklets and audio recordings
- Data collection forms
 - Hot Flash Daily Diaries
 - o Self-Hypnosis Practice Log
- Questionnaire booklets
 - o a compilation of all outcome questionnaires for data collection at Weeks 6 and 12
- Return-addressed mailers (for the return of study materials and data forms)

In the event that the randomization/education visit must take place through telephone or video conference due to COVID-19 restrictions, the Toolkit, containing the appropriate intervention materials, will be mailed or sent electronically to the participant prior to the randomization/education visit. Then, the participant will have these materials prior to the randomization/education visit, and these materials can be discussed in detail during the interaction.

The baseline Hot Flash Daily Diary, saliva, and the HRV monitor will be mailed to the lab at the end of the baseline week. These materials can also be submitted electronically if the randomization/education visit takes place by telephone or video conference during the COVID-19 restrictions. If the visit takes place in person (at a time when COVID-19 restrictions are not in place), it may be brought to the lab at the time of the randomization/education visit. Staff receiving the data will be blinded to group assignment of the participant returning the data collection materials, and data will be entered upon receipt by a blinded data collector.

Before week 6, a package will be mailed to the participant with cortisol collection materials and an HRV monitor. At the end of Week 6, participants will complete the outcome measures in the Questionnaire Booklet, a second 2-day cortisol collection and wear the HRV for the designated time at some point during the two-day cortisol collection period. Once the questionnaires and physiological data collection is complete, participants will return to the lab in a pre-paid mailer:

• Six, week-long Hot Flash Daily Diaries

- The Self-Hypnosis Practice Log
- Questionnaires Booklet
- Cortisol collection materials
- HRV monitor

However, if this collection was optional or unable to be completed due to COVID-19 restrictions, saliva samples and HRV data will not be collected at this time.

During Week 11, a phone call will be made to participants to remind them of the 12 week data collection which includes a 7-day Hot Flash Daily Diary, 7-Day Self-Hypnosis Practice Log, and self-report questionnaires. This will all be in the toolkit with a pre-paid mailer. At the end of the Week 12, participants will complete the questionnaires and return the Hot Flash Daily Diary, Self-Hypnosis Practice Log, and Questionnaire booklet.

Data collectors, individuals responsible for data entry, PIs, and the study statistician will be blinded to the participants' group assignment, but the research staff who will randomize and research assistants who will call participants will be aware of the participant's group assignment. Participants will also be blinded to the study hypotheses to avoid bias regarding what is the experimental treatment versus control arm.

All materials collected are for research purposes only, and data will be kept in strict confidence. No information will be given to anyone without permission from the participant. The consent form includes the informed consent statement required by NCCIH and Baylor University and University of Michigan IRBs for studies involving human subjects. This statement guarantees confidentiality and identifies the subject as the owner of the information received. Several methods will be used to protect participant confidentiality. Identifying information is separated from all data provided by participants through the use of randomly generated study identification code assigned to each participant. Identifying information that is collected on paper will be kept in a closed envelope in a locked file cabinet separate from the participant charts.

Only authorized research staff will have keys to the project file room.

In addition, all personnel will be trained in the importance of and measures to protect participant confidentiality according to Good Clinical Practice and ICH Guidelines. Signed confidentiality statements will be on file for every research staff member.

Analyses will include only summaries of data, and personal identifiers will be excluded.

All research staff involved in the design or conduct of this research will have demonstrated successful completion and certification in Human Subjects Protection Education.

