6.2.2.2 Baseline Assessments

Demographic Questionnaire & Health History Intake

The Demographic Questionnaire & Health History Intake is a brief intake questionnaire developed to capture participant characteristics, including age, race, ethnicity, education and similar demographics, time since first postmenopausal, history of breast cancer, and will be used to document no current use of alternative treatments for hot flashes.

Hot Flash Daily Diary

A Hot Flash Daily Diary will be used to measure the primary outcome of hot flash score. Participants will be asked to complete the Hot Flash Daily Diary every day for 6 weeks to measure the daily frequency and severity (mild, moderate, severe, and very severe) of hot flashes. Each level of severity is given a value; mild = 1; moderate = 2; severe =3; very severe = 4. Participates will rate the severity of each hot flash as they experience it and record it in their daily diary. A total hot flash score will be calculated for each participant (product of frequency x severity). For example, a woman with 3 mild and 2 severe hot flashes would have a hot flash score of 9 (3x1 = 3 + 2x3 =6). Participants are educated on how to collect hot flash information in real time throughout the course of each day. This process has been successfully used in numerous hot flash studies previously completed by [name] and colleagues^[75] and other investigators including [name]^[38, 39] and has yielded replicable data in trials by different groups who evaluated the same treatments ^[24] A hot flash diary will be provided to the participants at baseline and will be completed during the baseline week. A second diary will be provided for use during weeks 1 through 6 of the intervention period. A third hot flash diary will be used for week 12.

Hot Flash Related Daily Interference Scale (HFRDIS)

Participants will be asked to complete the Hot Flash Related Daily Interference Scale (HFRDIS) during baseline and weeks 6 and 12. This is a 10 item scale that measures hot flash interference.^[82] The HFRDIS asks respondents to rate the degree on a 0-10 scale that the hot flashes interfere with various daily activities as well as overall enjoyment or quality of life. This measure has been shown to be valid and internally consistent, with an alpha of .96.^[82] This will be completed at baseline, 6 and 12 weeks.

PROMISTM Emotional Distress – Anxiety Scale

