Previous research indicates that the EHS is highly correlated with longer measures of hypnotizability and has excellent reliability with a Cronbach's alpha of .94. [96] This will be administered to participants randomized to the hypnotic intervention group at the randomization visit. The [name] Hypnotizability Scale-Clinical Form (EHS-CF) will be administered during the randomization visit when the randomization visit takes place through telephone or video conference because of COVID-19 restrictions. The EHS-CF a less intensive and shorter version with 9 items compared to the full 12. However, this is not a different scale and provides the same measures we are seeking with a high correlation of .962 between the EHS and EHS-CF. The EHS-CF will allow for an easier implementation of the scale through remote procedures and be more user-friendly for the participants.

Self-Hypnosis Practice Log

Frequency of home practice is thought to be one of the moderators of the *efficacy* of hypnosis interventions^[70] and will be particularly important to collect for this self-administered protocol.^[70] Participants in both groups will be given a log that they will complete daily. The log will provide space to put the date, whether, or not the participant listened to their audio recording, the number of times they practiced (with and without the audio recordings), and

provide a space for comments about any interruptions or barriers to listening to their assigned recording. Between the log and the phone calls, the research assistant will be able to ascertain the degree to which women adhered to the protocol in terms of recording hot flashes in real time and using the audio-recordings as prescribed in the protocol. This will be completed daily during weeks 1 to 6 of the intervention and during week 12.

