6.2.3 Follow-up Visits

Week 1-6: Eligible participants will be randomly allocated to either a self-administered hypnosis group or a self-administered sham white noise hypnosis control group. Both groups will meet with a study research assistant two times (at baseline and at randomization/education visit) in person (or by telephone or video conference during COVID-19 restrictions) and further contact will be by phone through week 6 of the intervention period.

The interventions will be delivered through pre-recorded digital audio files, flash drives or CD's. For participants who prefer a flash drive or CDs, those will be provided. Additionally, if a participant prefers to use CDs, but does not have a CD player, one will be provided. Prepared self-management booklets will also be provided to each participant.

Participants in the self-administered hypnosis group and the self-administered sham white noise hypnosis group will use the self-management materials (booklets and audio recordings) for six weeks. A second kit to collect saliva and a Polar V800 HRV monitor will be mailed to participants during week five to be used for Week 6 data collection. At the end of Week 6, they will collect two days of saliva samples. HRV data will also be collected during the two days of saliva collection (as done during the baseline week) and both will be returned immediately following collection via a pre-posted mailer. However, if this collection was optional or unable to be completed due to COVID-19 restrictions, saliva samples and HRV data will not be collected at this time. At the end of Week 6, participants will return the completed hot-flash daily diaries, the self-hypnosis practice log, the questionnaire booklet with outcome measures of daily activity interference, quality of life, sleep disturbance, anxiety and stress in the provided pre-posted mailer. Due to COVID-19 restrictions, participants will also have the option of returning materials electronically (e.g., through DocuSign).

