Based upon our previous research (R34 AT008246-03) we anticipate minimal missing data on the primary outcome (hot flash scores) and drop-outs of 18% or less of those that start treatment; and the specific pattern of missing data found in our prior study was primarily toward the end of data collection. Therefore, in the present study some missing data is anticipated, particularly at follow-up (week 12). Our statistician has advanced experienced in R, Mplus, and SAS packages and has focused training in missing data analysis in Mplus and SAS. To handle missing data we will follow Little's (1995) recommendation by collecting multiple pieces of evidence for the tenability of missing completely at random (MCAR) assumption if we experience substantial (e.g., > 5%) missingness. That is, as appropriate we will (a) conduct Little's (1988) test of missing completely at random using the observed data as input, (b) test the equality of the distributions of each of the outcome measures with missing data patterns using t test for location, (c) compute the standardized mean difference in each of the outcome measures across missing data patterns, and (d) examine the distribution of demographic variables across missing data patterns. If the possibility of systematic bias is present, we will most likely consider a multiple imputation method using Mplus or SAS. Again, our statistician has experience and coding knowledge to conduct the analyses in either package. Additionally, we will collect multiple pieces of information that allow us to assess the extent to which excluding those who did not complete the entire protocol may introduce systematic bias. We note that missing data in longitudinal data collection studies has been referred to by Little and Rubin^[102] and Schafer and Graham^[103] as "monotone" because the missingness tends to appear toward the end of data collection rather than the beginning (as we anticipate based upon our prior studies). When the attrition mechanism does not depend on observed or unobserved outcome variables, the pattern can be described as completely random drop-out^[104] which is a special case of Rubin's^[105] MCAR assumption.^[106] We acknowledge that a standard mixed-model analysis or the use of HLM package will not handle different patterns of missing data on the six weeks of hot flash diaries or home practice logs. As noted, our statistician has experience and coding knowledge to conduct analysis in R, Mplus, and SAS packages and has focused training in missing data analysis in Mplus and SAS.

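### The week 1–6 hot flash diaries come back only once, after week 6, so a woman who leaves early can enter the primary model with only her baseline score

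*Combined protocol and SAP*

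**What the plan says.** - **Issue of the diary.** Section 6.2.2.2 gives the participant one diary for the whole treatment period: "A second diary will be provided for use during weeks 1 through 6 of the intervention period".
- **Return, Section 6.2.3 (Follow-up Visits).** "At the end of Week 6, participants will return the completed hot-flash daily diaries, the self-hypnosis practice log, the questionnaire booklet". Saliva and HRV are treated separately: "both will be returned immediately following collection via a pre-posted mailer". Nothing here makes the diary wait for them.
- **Return, Section 10.1.** "Once the questionnaires and physiological data collection is complete, participants will return to the lab in a pre-paid mailer". The contents listed are "Six, week-long Hot Flash Daily Diaries" together with the practice log, questionnaire booklet, saliva materials and HRV monitor. Read literally, the diary waits for the physiological measures.
- **Use of the data.** The primary model in Section 9.7 takes seven scores per woman, baseline plus weeks 1 to 6. Missing data are to be handled by multiple imputation, with comparisons of the outcome measures across missing-data patterns. On the expected pattern, it says that "the specific pattern of missing data found in our prior study was primarily toward the end of data collection".
- **Payment.** Section 6.2.4 makes the first payment once baseline and week-6 data collection are complete.

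The documents describe no interim return, no telephone transcription of scores, and no step to retrieve a partial diary from a woman who withdraws.

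**The concern.** All six post-baseline values of the primary outcome depend on one late return. A woman who stops in week 4 may have three good weeks of diary at home, and no scheduled step brings them in. She also has no payment reason to send them.

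Those early weeks are what make a missing-at-random assumption credible, because they show whether she was responding before she left. Without them, imputation gives her the course of a typical completer with the same baseline score and arm. The diagnostics in Section 9.7 cannot show whether leavers were failing treatment, because the only hot flash score they can compare is baseline. If women who do not benefit leave the hypnosis arm more often, the estimated benefit is too large.

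Under Section 10.1, primary-outcome data also wait on measures that matter only to the mediator analyses.

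**Working it through.** **1. The plan's own figures (Sections 9.3 and 9.7).** Effect size 0.41, 5% error (taken as two-sided), 80% power and 1:1 allocation give 95 per arm by the exact t calculation, so 190 in all (power 0.803). Then 190 / (1 − 0.18) = 231.7, rounded up to 232. Observations: 232 × 7 = 1,624. All agree with the plan.

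**2. Power.** If 18% of women lose everything after baseline, 232 × 0.82 = 190.2 remain and power is 0.803. The 232 already counts attrition as total loss. Parcel loss on top of that (assumed rates) gives 0.799 at 1% and 0.783 at 5%.

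**3. Exposure.** Post-baseline scores planned: 232 × 6 = 1,392.
- Upper bound (all 18% leave before the return and nobody mails a partial diary): 232 × 0.18 = 41.8, about 42 women; 41.8 × 6 ≈ 250 scores.
- Half the attrition after week 6 (assumption): about 21 women; 20.9 × 6 ≈ 125 scores.

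**4. What earlier return would keep.** Take the upper bound as 42 women and 42 × 6 = 252 scores, with dropout spread evenly over 0 to 5 completed weeks (assumption).
- Weekly return: 42 × 2.5 = 105 scores kept. The range is 42 to 210 if every leaver had completed 1 to 5 weeks.
- One return at day 21: half the leavers have completed at least three weeks, so 42 × 0.5 × 3 = 63 scores kept, before any sheets obtained at withdrawal.

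**5. Bias by direct calculation.** Assume the hypnosis arm is 65% responders (70% reduction) and 35% non-responders (13% reduction). The mean reduction is 0.65 × 0.70 + 0.35 × 0.13 = 0.5005. With 25% in sham, the true difference is 0.2505, or about 5.8 points on a baseline of 23. Let 18% drop out, let a share q of hypnosis-arm dropouts be non-responders, and let sham have no such selection. Baseline-only imputation returns the completers' mean, so

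bias = (0.70 − 0.13) × 0.18 × (q − 0.35) / 0.82 = 0.125 × (q − 0.35).

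Divided by 0.2505, the overstatement is about 0.50 × (q − 0.35):

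| q | Overstatement |
|---|---|
| 0.35 (dropout unrelated to response) | 0% |
| 0.50 | 7% |
| 0.60 | 12% |
| 0.87 | 26% |

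At q = 0.87, 0.18 × 0.87 / 0.35 = 45% of non-responders leave, against 0.18 × 0.13 / 0.65 = 3.6% of responders.

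**6. Illustrative simulations of the week-6 difference.**
- *Milder mechanism:* about 16% dropout, driven in the hypnosis arm by a poor previous week; SD of individual reduction 0.30; residual SD 3. Baseline-only imputation was off by 0.37 points on a true difference of 5.75 (0.37 / 5.75 ≈ 6%). Using all weeks before dropout left about 0.01 points.
- *Strong selection,* with the mixture in step 5: 26% from baseline only, 13% to 18% with weeks 1–3 in hand, and 8% to 14% with weeks 1–4 in hand.

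**The case against.** Several safeguards exist. A woman who stops can still post a partial diary, since the toolkit holds mailers. Section 8 follows women, with permission, after the intervention is discontinued. Section 3 provides administrative calls to confirm that data were sent and received. Section 6.2.3 allows electronic return during COVID-19 restrictions. The week 12 diary is returned separately, and the Manual of Procedures, which is not available here, may contain a retrieval step. These points stand, so the single return *can* remove a woman's post-baseline scores but need not. None of them sets an earlier return date, and the week 12 score is outside the primary model.

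Section 9.7 expects little missing primary-outcome data, with losses particularly at week 12, and losing all of weeks 1–6 after an observed baseline is still a monotone pattern. Both points stand. They make 42 women an upper bound and mean that the missing-data section is not formally contradicted.

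The bias figures concern the week-6 difference, while the planned test is the time-by-treatment slope over seven scores. They show direction and rough size only.

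A reader might also infer that Section 6.2.2.2 promises checks of the log during treatment, which a single return would prevent. Its words are "the research assistant will be able to ascertain the degree to which women adhered to the protocol in terms of recording hot flashes", and it names the log and the phone calls as the sources without giving a time. Asking on the calls and reading the log on return would satisfy it. The documents do not support a contradiction there.

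**Conclusion.** The point holds as an inexpensive improvement to data retrieval and bias control. The plan schedules one post-treatment return of the primary-outcome diaries, and Sections 6.2.3 and 10.1 disagree on whether it waits for saliva and HRV. For a woman who leaves early and sends nothing, imputation has only her baseline hot flash score as outcome history.

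Exposure is at most about 42 women and 250 of 1,392 scores, and about half that if half the attrition falls after week 6. The overstatement of roughly 6% to 26% assumes that hypnosis-arm non-responders leave more often, without matching selection in sham. It is zero if dropout is unrelated to response. The upper end needs about 87% of hypnosis-arm dropouts to be non-responders and should not be read as the expected bias.

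A reader might infer that the trial is underpowered as a result. It is not: 232 already allows for 18% total loss.

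**What to change.** Amend Sections 6.2.3 (Follow-up Visits) and 10.1, in the same words, so that:

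1. Completed diary sheets are returned at least once during treatment, for example weeks 1–3 at day 21 and the rest at day 42, by pre-paid mailer or the existing electronic route (made available outside COVID-19 restrictions). Weekly return is an option.
2. Diary return does not wait for saliva or HRV.
3. Women who withdraw are asked to send the sheets already completed. If the Manual of Procedures already has such a step, state it in the protocol.

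Also reconcile Section 6.2.3 (Blinding), where an unblinded staff member receives mailed data, with Section 10.1, where the staff receiving data are blinded. An added return makes it more important to settle this.

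Cost: one extra mailing per woman (232 in all), or five for weekly return (232 × 5 = 1,160), with logging and chasing at both sites and slightly more participant burden. Treatment, endpoint and sample size do not change.
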